238 The main research centres involved in the study are:

- 239 • Melbourne School of Population Health, University of Melbourne (managing institution)
- 240 • Kirby Institute, University of New South Wales
- 241 • Department of General Practice, University of Melbourne
- 242 • Institute of Social and Preventive Medicine, University of Bern

243 ***Contact details***

244 Associate [name]
245 Melbourne School of Population Health
246 University of Melbourne
247 [name]
248 [name]
249 [contact]
250 Email: [contact]

251 ***Aims and Objectives***

252 The study is a trial of the effectiveness of an intensive multifaceted intervention to increase rates of
253 annual chlamydia testing in primary care clinics (general practice clinics and AMSs). The hypothesis is
254 that by increasing testing rates to 30% of men and women aged 16 to 29 years, prevalence in clinic

255 attenders will decrease from about 4% to 2% in this population by the end of the trial period by the
256 end of the trial period.

257 ***Primary objective***

- 258 ● To determine whether an intervention to deliver organised regular chlamydia testing for
259 women and men aged 16 to 29 years who have ever had sex attending primary care clinics
260 (general practices and AMSs) leads to a reduction in estimated chlamydia prevalence in 16–
261 29-year old primary care attendees when compared with usual care.

262 ***Secondary objectives***

- 263 ● To determine whether an intervention to deliver organised regular chlamydia testing in
264 primary care clinics (general practices and AMSs) leads to a reduction in the incidence of PID
265 in 16–29-year old primary care attendees.
- 266 ● To determine whether an intervention to deliver organised regular chlamydia testing in
267 primary care clinics (general practices and AMSs) leads to a reduction in the incidence of
268 epididymitis in 16–29-year old primary care attendees.
- 269 ● To determine whether an intervention to deliver organised regular chlamydia testing in
270 primary care clinics (general practices and AMSs) can increase chlamydia testing rates.
- 271 ● To determine the proportion of individuals tested who return for a repeat test 12 months
272 after a previous negative test result.
- 273 ● To determine the proportion of individuals tested who return for a repeat test three months
274 after a positive chlamydia test result.

275 ***Design***

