- 345 • Language barrier, intoxication, incapacitation (e.g. severe illness), intellectual difficulty, or
346 other circumstances that hinder a patient’s ability to give informed consent.

347 ***Intervention***

348 ***Multifaceted chlamydia screening intervention***

349 The intervention is an organised programme for the delivery of annual chlamydia testing and
350 treatment in general practices and AMSs in Australia. Clinics will receive a multifaceted intervention
351 package that will encourage staff to offer chlamydia testing to all eligible patients in the target
352 population. The intervention package has been designed to be delivered and evaluated as a whole,
353 with the logistics of implementation tailored to the needs and resources of each clinic. The
354 components of the intervention package include:

- 355 • Chlamydia and PID education package for GPs and other clinic staff. This provides a number
356 of strategies for introducing chlamydia testing during a consultation; health education and
357 promotion materials for health care providers and patients; guidelines to facilitate the
358 consistent application of clinical criteria for the diagnosis of PID and epididymitis; and
359 information on effective partner notification.

- 360 • A computer alert programmed into the practice patient management system or as part of a
361 separate consulting sidebar tool (www.racgp.org.au/what-is-sidebar/), prompting
362 GPs or other clinic staff to discuss chlamydia testing with eligible patients.
- 363 • A patient reminder system within the practice patient management system that will recall
364 tested patients via letter, phone or SMS after 12 months if chlamydia negative and after
365 three months if chlamydia positive.
- 366 • Feedback on testing rates provided every three months in the form of quantitative reports,
367 showing the GP's quarterly chlamydia testing rates over time.
- 368 • GP incentive payments: \$5 per eligible patient tested up to 20% of eligible patients tested;
369 \$7 per eligible patient tested for >20% to 40% of eligible patients tested; \$8 per eligible
370 patient tested for >40% of eligible patients tested. Payments will be made every three
371 months to the GP ordering the test.
- 372 • Practice nurse (PN) incentive payments: clinics will receive an additional \$10 payment per
373 test conducted if a PN discussed chlamydia testing with a patient and initiates a test. The

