488 reporting text in the medical records. STI test results associated with the epididymitis diagnosis will
489 be extracted and linked with the epididymitis diagnosis.

490 **Testing uptake rates**

491 Testing uptake per year (with 95% CI) of eligible patients will be assessed in intervention and control
492 groups as an overall measure, as well as stratified by sex, age group (16 to 19, 20 to 24, 25 to 29
493 years) and Aboriginal and/or Torres Strait Islander status. The numerator will be the number of
494 individuals aged 16 to 29 years who were tested for chlamydia at least once in the past year; the
495 denominator will be the number of unique individuals aged 16 to 29 years who had a consultation
496 with a GP at the clinic in the past year. The denominator will include patients who have not had
497 sexual intercourse, as this information is not recorded on patient records. The Australian Study of
498 Health and Relationships [87] or similar up-to-date data will be used to adjust denominators for the
499 proportion likely to be sexually active.

500 **Annual re-testing rate**

501 Overall annual re-testing of eligible patients will be determined in intervention and control clusters,
502 and stratified by sex, age group (16 to 19, 20 to 24, 25 to 29 years) and Aboriginal and/or Torres
503 Strait Islander status. The numerator will be the number of individuals aged 16 to 29 years who were
504 tested for chlamydia 12 months (allowable range 10 to 15 months) after a previous chlamydia test;
505 the denominator will be the number of unique individuals aged 16 to 29 years who had at least one

506 chlamydia test in the previous year. The Australian Study of Health and Relationships [87] or similar
507 up-to-date data will be used to adjust denominators for the proportion likely to be sexually active.

508 **Test for repeat infection**

509 Tests for repeat infection in eligible patients following a positive chlamydia diagnosis will be
510 measured overall in intervention and control clusters, and stratified by sex, age group (16 to 19, 20
511 to 24, 25 to 29 years) and Aboriginal and/or Torres Strait Islander status. The numerator will be the
512 number of individuals aged 16 to 29 years re-tested for chlamydia three months (allowable range six
513 weeks to six months) after a positive test; the denominator will be the number of unique individuals
514 aged 16 to 29 years who tested positive for chlamydia in the previous year.

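### The annual re-testing endpoint accepts any previous test, whereas its objective and the 12-month recall concern people with a negative result; the effect is small

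*Protocol*

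**What the plan says.** The points below are all in the protocol; no separate statistical analysis plan was available.

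- **Secondary objectives.** One objective reads "To determine the proportion of individuals tested who return for a repeat test 12 months" "after a previous negative test result". A separate objective covers return three months after a positive result.
- **Intervention, multifaceted screening package.** The reminder system recalls "tested patients via letter, phone or SMS after 12 months if chlamydia negative and after" "three months if chlamydia positive". The two results lead to two different recall intervals.
- **Secondary endpoints, Annual re-testing rate.** The numerator is individuals aged 16 to 29 "tested for chlamydia 12 months (allowable range 10 to 15 months) after a previous chlamydia test". For the denominator, "the denominator will be the number of unique individuals aged 16 to 29 years who had at least one" "chlamydia test in the previous year". Neither part mentions the result of the earlier test.
- **Secondary endpoints, Test for repeat infection.** Re-testing of positives has its own endpoint, conditioned on a positive test, with an allowable window of six weeks to six months.
- **Statistical tests.** Annual re-testing rates are to be summarised by randomised group and compared with hierarchical models.

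**The concern.** The objective and the recall schedule both split people by the result of the earlier test, and the endpoint for positives keeps that split. The annual endpoint alone does not. An analyst who follows its definition would report a rate in a mixed population, and a reader would take it as the answer to an objective about negatives.

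The mixing works in both directions. A positive who returns on schedule at about three months gains nothing in the annual numerator from that visit, yet stays in the denominator. A positive who misses the three-month visit and next appears at 10 to 15 months is credited as an annual re-test, although the objective does not concern that person's return.

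The definition also refers only to a previous test, without saying which one. People with several tests, which the three-month recall is meant to produce, could be scored differently by different analysts.

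**Working it through.** The protocol gives no expected rate, target or power for this endpoint, so there is no figure to reproduce. The check is a comparison of definitions, followed by a bound on the size of the mismatch.

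**Definitions side by side**

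| Element | Objective | Endpoint |
|---|---|---|
| Earlier test | negative | any result |
| Denominator | implied: people with a negative test | everyone with at least one test in the previous year |
| Counted re-test | at 12 months | 10 to 15 months after a previous test |

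**Timing for a positive at month 0**

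1. The scheduled repeat test falls between 1.5 and 6 months. That is wholly below 10 months, so it cannot count from the positive test.
2. Repeat test at month 3, next test 12 months later at month 15: this is 15 months from the first test and 15 − 3 = 12 from the second. Both lie within 10 to 15, so the person is a success.
3. Repeat test at month 4, next test 12 months later at month 16: this is 16 months from the first test (outside the window) and 16 − 4 = 12 from the second (inside). The score depends on the anchor, which is not stated.
4. No repeat test, then a test at month 12: this counts as a success, although the earlier result was positive.

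**Size**

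Let p be the share of the denominator that is positive, r the 10-to-15-month re-test rate in negatives, and q that rate in positives. Then

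measured rate = (1 − p)·r + p·q,

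while the objective asks for r. The difference is p·(r − q), and its largest downward value, at q = 0, is p·r, a relative loss of p.

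Inputs: p = 3 to 5% is the protocol's prevalence range for this age group (background section on young heterosexual adults in Australia), used as a proxy for positivity among those tested. r = 30% and all values of q are assumptions.

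| p | q = 0 | q = r/2 = 15% | q = r = 30% |
|---|---|---|---|
| 3% | 0.97 × 30 = 29.1% | 29.1 + 0.45 = 29.55% | 30% |
| 4% | 0.96 × 30 = 28.8% | 28.8 + 0.60 = 29.4% | 30% |
| 5% | 0.95 × 30 = 28.5% | 28.5 + 0.75 = 29.25% | 30% |

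The worst case is 0.9 to 1.5 points, or 3 to 5% relative. If positivity among those tested were 10% (assumed), the worst case would be 0.90 × 30 = 27.0%. If q exceeded r, the measured rate would be too high.

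**Between arms**

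Assume r = 20% in both arms, q = 0, and positivity of 2% in one arm and 4% in the other. The rates are 0.98 × 20 = 19.6% and 0.96 × 20 = 19.2%, an artificial difference of 0.4 points. With equal positivity and equal q in the two arms, the formula gives the same measured rate in both, so no difference arises.

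**The case against.** The strongest defence is that an overall annual re-testing rate is a sensible quantity. Annual testing is recommended for sexually active people under 30, and the trial targets all eligible 16-to-29-year-olds for it whatever their past result. Someone with an earlier positive remains due for annual testing, so the wording of the objective could be changed instead. This is a legitimate alternative, but the protocol does not take it: objective and endpoint stand unreconciled.

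The defence is also right on size. This is a secondary process measure with no power calculation or decision rule resting on it, and the distortion disappears if positives re-test like negatives.

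Three stronger readings are tempting and are not supported:

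- **That positives are scored as failures, or that following the recall schedule is penalised.** Someone tested at months 0, 3 and 15 is inside the window from either earlier test.
- **That positives with a test late in the year are lost because their annual test falls beyond the following year.** The endpoint sets no calendar limit on the re-test; the reference to the previous year defines only the denominator. Nor does the protocol say that a positive who misses the three-month visit gets no later reminder. It is silent on this.
- **That the comparison between arms is biased.** This needs positivity among those tested to differ by arm and positives to re-test differently from negatives. The protocol gives no figure for either.

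**Conclusion.** The endpoint is wrong as written, with a small effect. Followed literally, it yields a rate in everyone previously tested, while the objective and the 12-month recall concern people with a negative result, and nothing in the protocol reconciles the two.

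At 3 to 5% positivity, the rate is at most 3 to 5% too low in relative terms. That bound assumes that prevalence stands in for positivity among those tested, and that no positive is tested in the window. It is a ceiling, because some positives will be, and because those with a negative repeat test in the same year also belong to the population of the objective. The case for a change rests on the contradiction, the unstated anchor test and the low cost of repair. It does not rest on the size of the bias.

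**What to change.** Redefine the Annual re-testing rate as follows:

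- **Denominator:** unique individuals aged 16 to 29 with at least one negative test in the previous year.
- **Anchor:** one stated test per person, for example the first negative test in that year. A negative three-month repeat test qualifies, so that people who were positive and then negative are not dropped; they meet the objective.
- **Numerator:** those in the denominator tested 10 to 15 months after the anchor.
- **Data source:** linked, coded extraction data only. The backup pathology and Medicare counts carry no unique identification code (Data collection section), so the endpoint should not be computed from them.
- **Supplementary figure:** the rate after any previous test may be kept, split by the previous result.

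The cost is a change of wording in one endpoint and a slightly smaller denominator. At 3 to 5% positivity the denominator falls by at most that share, and by less where positives have a negative repeat test in the year. Results linked to individuals are already needed for the repeat-infection endpoints, so no new data collection is required.

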200 the harms at reasonable cost. There is ongoing debate about the effectiveness of chlamydia
201 screening in controlling transmission and preventing complications, based on the results of
202 controlled trials [73]. Evaluating chlamydia screening compared with no screening is not possible,
203 given existing recommendations. Interventions to increase the uptake of regular chlamydia testing
204 above levels achieved through routine health services should be evaluated.

205 There is reason to believe that an organised programme of screening for chlamydia could be
206 effective. Mathematical modelling suggests that systems that ensure high levels of annual chlamydia
207 testing, treatment and partner notification are needed to interrupt transmission and reduce
208 chlamydia prevalence sustainably [74]. These levels of testing have been achieved through a
209 multifaceted intervention in paediatric clinics reported by Shafer and colleagues [61].

210 General practice is well placed as a setting for chlamydia screening; in Australia, 90% of women and
211 70% of men aged 15–24 years present to a general practitioner (GP) each year [75]. Levels of general
212 practice attendance are similar in the UK [76]. In addition, a large proportion of diagnosed chlamydia
213 cases are notified from general practice [52]. Research with Australian GPs shows that they believe
214 that general practice is an appropriate place for chlamydia screening to take place [77, 78]. They also
215 cite factors that could facilitate increased chlamydia testing, including chlamydia education for
216 providers and the community, incentive payments, increasing the role of practice nurses,
217 recall/reminder registers and resources to help with partner notification. In Australia, 15.7% of

218 practice nurses have attained post-registration accreditation to perform Pap screening, and 20.7%
219 report regular involvement in women's healthcare including pap smears, breast care, fertility, and
220 menopause [79]. This suggests that there is capacity for practice nurses to increase their
221 involvement in chlamydia testing and management, including maintaining clinic resources and recall
222 lists and assisting with discussions with patients around partner notification and safer sex practices.

223 Annual chlamydia testing for sexually active men and women under 30 years is recommended in
224 Australia [80], yet testing rates remain low with 8% of 15 to 29 year olds testing each year.

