596 appropriate. There will be no statistical hypothesis tests for this comparison.

597 ***Type of analysis***

598 Primary analyses of the trial endpoint will be according to the intention to treat principle, with
599 clusters analysed according to their randomised group, regardless of the level of uptake of the
600 intervention. Secondary analyses of the measurement outcomes will explore the effect of adherence
601 to the intervention, first by excluding clusters with poor adherence, and second by regression of
602 measures of cluster adherence on outcomes.

603 ***Statistical tests***

604 Formal statistical comparisons will be based on generalised mixed models that can account for
605 cluster, clinic and participant variability. Generalised estimating equation (GEE) approaches, with
606 robust standard errors, will be adopted using STATA statistical software (StataCorp, College Station,
607 TX, USA). Initial analyses will be simple, unadjusted comparisons of randomised areas. If there
608 appear to be any important imbalances between randomised groups in terms of baseline covariates,
609 adjusted analyses will also be performed, and presented in addition to unadjusted comparisons. The
610 impact of other potential confounding factors such as age and gender of the patients and GPs, and
611 socio-economic profile of the area served by the clinic will also be investigated in this analysis. The
612 difference between intervention and control clusters will be estimated, with 95% confidence
613 intervals and p-values from the corresponding hypothesis tests. Statistical significance will be taken
614 as a two-sided p-value less than 0.05, with no adjustment for multiple comparisons.

615 Outcome measures will be assessed as follows:

- 616 • Chlamydia prevalence in clinic attenders after the intervention period will be summarised by
617 randomised group, and by sex and age group. Formal comparisons will be based on
618 hierarchical logistic regression models.
- 619 • Incidence of PID per 100 female patients seen at a clinic will be summarised by randomised
620 group and by age group. Analyses will be based on Poisson regression models.
- 621 • Incidence of epididymitis per 100 male patients seen at a clinic will be summarised by
622 randomised group and by age group. Analyses will be based on Poisson regression models.

- 623 • Testing uptake rates, testing coverage, annual re-testing rates, testing for reinfection and

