624 rates of re-infection will be summarised by randomised group and compared using
625 appropriate hierarchical models.

626 ***Planned subgroup analyses***

627 The effect of the intervention within different subgroups of clusters will be explored, but interpreted
628 cautiously given the relatively small number of clusters. Subgroups may include sex, age group, area
629 type, Aboriginal and/or Torres Strait Islander status, estimated baseline chlamydia prevalence and
630 baseline testing rate. Intervention and control clusters will be compared within each subgroup and
631 evidence for heterogeneity of effects assessed using tests for interaction between randomised
632 intervention and subgroup. The effect of GP and clinic characteristics on testing uptake, annual
633 retesting rates, retesting after a positive diagnosis and chlamydia prevalence will be investigated.
634 The impact of patients attending from an area outside of the cluster will be investigated by analysing
635 patient postcode and its association with chlamydia prevalence.

636 ***Ethical issues***

637 ***Ethics committee approval***

638 The ACCEPt trial has been approved by the RACGP National Research and Evaluation Ethics
639 Committee and the University of Melbourne Human Research Ethics Committee. Approval has also
640 been obtained from the Aboriginal Health and Medical Research Council (AHMRC) Ethics Committee
641 to conduct the ACCEPt trial in AMSs. Specific services may also request ethical approval be sought
642 from local ethical committees.

643 ***Informed consent and information sheets***

644 ACCEPt research staff will explain the data collection requirements of the trial to all clinic staff prior
645 to them providing informed consent. Informed consent will cover all data collection activities of the
646 trial, recognise the principles of confidentiality and data ownership and define processes for
647 reporting of findings and release of trial results. A plain language participant information sheet will
648 be provided, which summarises the trial, participation requirements, confidentiality and disclosure
649 of information, and ethics approval and complaints contacts.

650 GPs can withdraw from the trial by notifying ACCEPt staff at any time and completing a withdrawal
651 of informed consent form. Unless otherwise requested, data collected from the clinic up until the

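### The re-testing endpoints are compared between arms among people already tested or already positive, groups the intervention is designed to change, so the difference mixes return with selection in an unknown direction

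*Protocol*

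**What the plan says.** Under Secondary endpoints (Annual re-testing rate), the numerator is people re-tested at 12 months (allowed range 10 to 15) and "the denominator will be the number of unique individuals aged 16 to 29 years who had at least one" chlamydia test in the previous year. Under Test for repeat infection, the numerator is people re-tested six weeks to six months after a positive result, and the denominator is people "aged 16 to 29 years who tested positive for chlamydia in the previous year". By contrast, the uptake endpoint just above uses everyone aged 16 to 29 with a GP consultation in the year.

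The Statistical tests section makes these between-arm comparisons: "Testing uptake rates, testing coverage, annual re-testing rates, testing for reinfection and" "rates of re-infection will be summarised by randomised group and compared using" suitable hierarchical models. The same section attaches 95% confidence intervals and two-sided p-values at 0.05, without multiplicity adjustment.

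The intervention acts at two stages. The computer alert prompts "GPs or other clinic staff to discuss chlamydia testing with eligible patients", supported by education, incentive payments and feedback; this changes who is tested. The reminder system recalls "tested patients via letter, phone or SMS after 12 months if chlamydia negative and after" three months if positive; this acts on return.

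**The concern.** Being tested, and therefore being found positive, is an outcome of allocation. Randomisation makes the attenders of the two arms comparable, but not the attenders who happen to be tested. If the intervention works as intended, its denominators hold the people who would have been tested anyway plus a larger number tested only because of the programme. If those added people return at a different rate, the two proportions differ even when recall does nothing, and a real effect on return can be diluted, reversed or inflated.

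The first trial year is a partial exception, because the previous year's tests may predate randomisation. After that the denominators are formed under the intervention.

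Two stated secondary objectives concern re-testing, and the trial's rationale depends on testing being repeated. A p-value on this contrast would invite a causal reading that the design does not support.

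**Working it through.** The Protocol gives no target, effect size or power for the re-testing endpoints, so there is no figure to reproduce. The check asks how far a change in composition can move the planned comparison.

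**Inputs from the Protocol**
- Usual-care testing of 8% a year (Rationale for the trial): "Australia [80], yet testing rates remain low with 8% of 15 to 29 year olds testing each year". This is a rate for 15 to 29 year olds, not a baseline for trial clinics.
- Target testing of 30% (Aims and Objectives): "that by increasing testing rates to 30% of men and women aged 16 to 29 years, prevalence in clinic" attenders is expected to fall.
- Re-testing after a positive in general practice: 26.4% within 1.5 to 4 months (Rationale for the trial).

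**Assumptions, not in the Protocol**
- r: return rate of people who would be tested anyway.
- g: how much lower the added testers' unaided return is (negative if higher).
- d: points that recall adds for everyone.
- The 8 per 100 tested under usual care are also tested under the intervention.

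**Annual re-testing**

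Control = r. Intervention = (8/30)(r + d) + (22/30)(r − g + d). Difference = d − (22/30)g.

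With r = 20% and d = 5 points:

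| Added testers' unaided return | g | Intervention | Difference from 20% |
|---|---|---|---|
| 5% | 15 | 14.0% | −6.0 |
| 10% | 10 | 17.7% | −2.3 |
| 15% | 5 | 21.3% | +1.3 |
| 20% | 0 | 25.0% | +5.0 (no bias) |
| 30% | −10 | 32.3% | +12.3 |

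The sign reverses when g > d × 30/22 = 1.36d, which is 6.8 points for d = 5. If uptake reaches only 20%, the added share is 12/20 and reversal needs g > 1.67d. At 12% uptake the share is 4/12 and it needs g > 3.0d.

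**Testing after a positive**

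Take r = 26.4%, d = 5 and g = 10. If added testers have the same positivity as usual testers, the intervention proportion is 26.4 + 5 − (22/30) × 10 = 24.1%. If they have half the positivity (assumed), the weights are 8 and 22 × 0.5 = 11, the added share is 11/19 = 58%, and the proportion is 26.4 + 5 − (11/19) × 10 = 25.6%. Reversal then needs g > (19/11)d = 1.73d.

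**What an all-attender denominator shows**

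Re-tested people per 100 attenders, with r = 20% and added testers at 10% unaided:
- Control: 8 × 0.20 = 1.6.
- Intervention, d = 5: 8 × 0.25 + 22 × 0.15 = 5.3.
- Intervention, d = 0: 8 × 0.20 + 22 × 0.10 = 3.8.
- Intervention, d = −3: 8 × 0.17 + 22 × 0.07 = 2.9.

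This measure captures the whole package and cannot isolate recall.

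For repeat-tested positives per 1000 attenders, assume positivity equal to the hypothesised prevalences (4% and 2%) and 26.4% return in both arms. The result is 80 × 0.04 × 0.264 = 0.84 against 300 × 0.02 × 0.264 = 1.58. The figure nearly doubles with no change in return, and it depends on prevalence, which is the primary outcome.

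**The case against.** The strongest reply has four parts.

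1. **Direction.** A reader might infer that the added testers, being mostly without symptoms, return less readily, so the comparison will understate or reverse the benefit. The Protocol gives no return rates by reason for testing. Control clinics also work under guidance recommending annual testing, so their testers may be partly asymptomatic too. The Rationale does report re-testing after a positive of 8.6% to 17.8% across patient groups at sexual health services, so return varies with who was tested, but those groups are not defined by reason for testing. This objection stands: no direction can be claimed. The illustration also uses the widest contrast, a hypothesised 30% against an 8% that does not come from trial clinics.

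2. **Importance.** The secondary objectives ask only for the proportion of tested people who return, and the denominators match that. The Summary lists PID, epididymitis and uptake as secondary outcomes, without re-testing. The package is to be evaluated as a whole. This stands as a limit on weight, but it does not defend the formal comparison, which goes beyond those objectives.

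3. **Existing handling.** Results are stratified by sex, age group and Aboriginal and/or Torres Strait Islander status, and patient age and gender are to be examined as confounders. That removes part of the difference, but not selection by symptoms, risk or reason for testing. The claim that automated extraction reduces bias concerns measurement only.

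4. **Remedy.** An all-attender comparison rises with uptake even if recall is useless. This is correct, so that comparison must be labelled for what it measures. For positives, the dependence on prevalence is enough to rule out a formal test.

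**Conclusion.** The point holds as a matter of structure. Both re-testing endpoints are compared between arms within groups formed largely after randomisation, by an event the intervention is designed to change. The difference is therefore not an estimate of the effect on return.

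Size and direction cannot be fixed from the Protocol. At the target uptake, each point by which added testers' return falls below (or exceeds) that of usual testers lowers (or raises) the apparent effect by 22/30 = 0.73 points; at lower uptake the distortion is smaller. With equal return there is none. A wrong sign is possible but not established. The figures rest on 8% and 30% testing, an equal recall effect in both types of patient, and assumed return rates.

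The point concerns secondary endpoints only. Nothing here touches the prevalence comparison or the within-arm description of re-testing.

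**What to change.** - Report the proportions re-tested among those tested, and among positives, by arm as descriptive results: estimates with 95% confidence intervals, no p-value and no causal claim. This meets both secondary objectives.
- For annual re-testing, make the formal between-arm comparison on all 16 to 29 year olds with a consultation in the index year. The outcome is an index test plus a re-test at 10 to 15 months, per 100 attenders. Label it as the effect of the whole package on sustained annual testing, not of recall alone, and present it beside uptake.
- Do not formally test repeat-tested positives per 1000 attenders, because that figure also moves with uptake and with chlamydia prevalence.

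The cost is wording in the endpoint and analysis sections. The same linked consultation and testing records suffice. The price is interpretive: the all-attender measure combines first testing with return and rises with uptake even when recall has no effect, so a gain on it must not be reported as evidence that recall works.
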